##### **3.6.1.4 Pharmacokinetic Per Protocol Set**

Two different Pharmacokinetic Per Protocol Sets (PK-PPS) will be generated (1 for each device type): the bimekizumab-SS-1mL PK-PPS (PK-PPS-s) and the bimekizumab-AI-1mL PK-PPS (PK-PPS-a). Each PK-PPS will consist of all subjects who receive the same bimekizumab administration (frequency and dose) in the PS0014 feeder studies as in the DV0002 substudy and who have at least 1 evaluable PK assessment in the DV0002 substudy without important protocol deviations that would affect the concentration. Pharmacokinetic variables will be analyzed using the PK-PPS-s and PK-PPS-a.

All PK assessments after baseline assessments from feeder study will be considered for the requirement of at least one evaluable PK assessment.

#### **3.6.2 2mL Device Cohort**

##### **3.6.2.1 Enrolled Set**

The Enrolled Set (ES) will consist of all subjects who have given informed consent for DV0002.

##### **3.6.2.2 Safety Set**

Two different Safety Sets (SS) will be generated (1 for each device type): the bimekizumab-SS-2mL Safety Set (SS-s) and the bimekizumab-AI-2mL Safety Set (SS-a). Each SS will consist of all subjects in the study who receive at least 1 dose of bimekizumab by the indicated self-injection investigational device. Safety variables will be analyzed using the SS-s and SS-a.

##### **3.6.2.3 Full Analysis Set**

Two different Full Analysis Sets (FASs) will be generated (1 for each device type): FAS-s and FAS-a. Each FAS will consist of all subjects in the SS-s or SS-a who self-inject at least 1 dose of

bimekizumab using the given device and who have an assessment of self-injection. All self-injection related endpoints will be analyzed using the FAS-s and FAS-a.

### **3.6.2.4 Pharmacokinetic Per Protocol Set**

Two different Pharmacokinetic Per Protocol Sets (PK-PPS) will be generated (1 for each device type): the bimekizumab-SS-2mL PK-PPS (PK-PPS-s) and the bimekizumab-AI-2mL PK-PPS (PK-PPS-a). Each PK-PPS will consist of all subjects who receive the same bimekizumab administration (frequency and dose) from beginning of PS0014 through to the end of the study and who have at least 1 evaluable PK assessment in the DV0002 substudy without important protocol deviations that would affect the concentration. Pharmacokinetic variables will be analyzed using the PK-PPS-s and PK-PPS-a.

All PK assessments after DV0002 baseline assessments (Week 24, Week 28 or Week 32 from PS0014 study) will be considered for the requirement of at least one evaluable PK assessment.

## **3.7 Treatment assignment, treatment and device groups**

This is an open-label study and as such all subjects will be summarized according to the treatment that was provided. The treatment group will be allocated in PS0014 and the device group will be allocated in DV0002.

### **PS0014 treatment groups**

This refers to the study treatment assigned to the subject at the beginning of PS0014 and does not account for the treatment received in the relevant Feeder Study. The allocation of treatments in PS0014 is done by an algorithm considering the subjects' feeder study (PS0008, PS0009, or PS0013) and PASI90 response at PS0014 study entry. The PS0014 treatment groups are as follows:

- Bimekizumab 320mg Q8W
- Bimekizumab 320mg Q4W.

### **DV0002 device groups**

This refers to the study device assigned to the subject at the beginning of DV0002. The DV0002 1mL device groups are as follows:

- Bimekizumab-SS-1mL
- Bimekizumab-AI-1mL.

The DV0002 2mL device groups are as follows:

- Bimekizumab-SS-2mL
- Bimekizumab-AI-2mL.

The outcome variables will be summarized by PS0014 treatment and DV0002 device group. The different DV0002 device groups are reflected in the use of the corresponding analysis set SS-s, SS-a, FAS-s, FAS-a, PK-PPS-s and PK-PPS-a. For simplification "treatment group" and "device group" will be used in the outputs.

### **3.8 Center pooling strategy**

No pooling of centers is planned for this study.

### **3.9 Coding dictionaries**

All ADEs will be coded and classified by system organ class (SOC), high level term (HLT), and preferred term (PT) according version 19.0 of the Medical Dictionary for Regulatory Activities (MedDRA®).

All medications other than the study drug will be classified by World Health Organization (WHO) Anatomical Therapeutic Chemical (ATC) classification, presenting Anatomical Main Group (ATC Level 1), Pharmacological Subgroup (ATC Level 3), and preferred term (PT), using version SEP/2015 of the World Health Organization Drug Dictionary (WHO-DD), according to UCB standard operating procedures (SOP).

Previous and ongoing medical history will be classified by version 19.0 of MedDRA® SOC and PT.

### **3.10 Changes to protocol-defined analyses**

Subjects who had important protocol deviations affecting the primary outcome variable, as confirmed during ongoing data cleaning meetings prior to database lock, will be not excluded from the FAS-s or FAS-a.

#### **3.10.1 Changes related to COVID-19**

COVID-19 protocol deviations have been defined in Section 3.5 and the presentation of COVID-19 protocol deviations is described in Section 5.3.

## **4 STATISTICAL/ANALYTICAL ISSUES**

### **4.1 Adjustments for covariates**

Not applicable.

### **4.2 Handling of dropouts or missing data**

For analyses of ADEs and concomitant medication usage, a complete date must be established in order to correctly identify the ADE or medication as occurring during treatment or not. To calculate the duration of disease, a complete date of onset of plaque psoriasis is needed. For purposes of imputing missing components of partially-reported start and stop dates for ADEs, for medication use, and date of onset of plaque psoriasis, the algorithms listed below will be followed. Start and stop dates of ADEs or concomitant medication will be displayed as reported in the subject data listings (i.e., no imputed values will be displayed in data listings).

Partial ADE and concomitant medication start dates will be imputed as follows:

#### **Imputation of Partial Start Dates**

- If only the month and year are specified and the month and year of first dose is not the same as the month and year of the start date, then use the 1st of the month
- If only the month and year are specified and the month and year of first dose is the same as the month and year of the start date, then use the date of first dose

- If only the year is specified, and the year of first dose is not the same as the year of the start date, then use the 1st of January of the year of the start date
- If only the year is specified, and the year of first dose is the same as the year of the start date, then use the date of first dose
- If the start date is completely unknown and the stop date is unknown or not prior to the date of first dose, then use the date of first dose.

#### Imputation of Partial Stop Dates

- If only the month and year are specified, then use the last day of the month
- If only the year is specified, then use December 31st of that year
- If the stop date is completely unknown, do not impute the stop date.

If the (imputed) stop date is prior to the imputed start date:

- If only the month and year are specified and the month and year of first dose is the same as the month and year of the start date and the stop date is before the date of first dose, then set the start date to the 1st of that month.
- If only the year is specified, and the year of first dose is the same as the year of the start date, and the stop date is before the date of first dose, then use the 1st of January of the year of the start date

Partial start dates for onset date of plaque psoriasis will be imputed as follows:

- If only the month and year are specified, then use the last day of the month.
- If only the year is specified, then use the 31st of December of the year.
- If the start date is completely unknown, do not impute the start date.

In the event of ambiguity or incomplete data which makes it impossible to determine whether a medication was concomitant or an adverse event was treatment emergent, the medication will be considered as concomitant or the adverse event will be considered treatment emergent.

If the intensity of an ADE is unknown, it will be considered as severe.

There will be no special procedures for handling missing data for any other data points.

### **4.3 Interim analyses and data monitoring**

No interim analysis is planned for this study. No Data Monitoring Committee will be established for this study.

The subjects of DV0002 are ongoing subjects of PS0014. Data cut off for the 1mL final analysis will be last subject last Week 16 visit in DV0002 in the 1mL device cohort. Data cut off for the 2mL final analysis will be last subject last Week 16 visit in DV0002 in the 2mL device cohort. Data cut off rules will be applied for ongoing adverse device events and ongoing concomitant medication.

#### **4.4 Multicenter studies**

Individual center results will not be directly presented. Centers are only located in North America (United States and Canada).

#### **4.5 Multiple comparisons/multiplicity**

Not applicable.

#### **4.6 Use of an efficacy subset of subjects**

Not applicable.

#### **4.7 Active-control studies intended to show equivalence**

Not applicable.

#### **4.8 Examination of subgroups**

Not applicable.

### **5 STUDY POPULATION CHARACTERISTICS**

#### **5.1 Subject disposition**

All subject disposition tables will use the PS0014 treatment groups BKZ 320mg Q8W and BKZ 320mg Q4W and an overall treatment group category (BKZ Total).

The disposition of subjects including the number of subjects in ES and all device-specific analysis sets (SS-s, FAS-s, PKS-s or SS-a, FAS-a, PKS-a) will be summarized. This summary will be based on ES and will present subjects overall and by site in North America.

The disposition of ES will present all bimekizumab treated subjects by PS0014 treatment group and broken out by DV0002 device group.

The number and percentage of subjects who entered the substudy, completed, discontinued with the reasons for discontinuation of the substudy will be presented. This summary will be based on the ES and will present all bimekizumab treated subjects by PS0014 treatment group and broken out by DV0002 device group.

Subjects will be counted as completer if they completed the DV0002 Week 16 visit.

The following listings for subject disposition will be produced based on the ES and presented by PS0014 treatment group/ DV0002 device group:

- A listing of subjects who did not meet study eligibility criteria
- A listing of subject disposition
- A listing of study discontinuation
- A listing of visit dates
- A listing of subjects excluded from analysis sets.
- A listing of subject analysis sets

## 5.2 Protocol deviations

A summary of number and percentage of subjects with an important protocol deviation (including a summary of subjects excluded from any analysis set due to important protocol deviations) by treatment group will be provided for the SS-a and SS-s.

A by-subject listing of important protocol deviations will be provided.

## 5.3 COVID-19 Impact

For study participants impacted by the COVID-19 global pandemic, data were collected on a separate eCRF. This form was collected for study visits that were affected by COVID-19, and it collected how the visits were impacted by the pandemic (e.g., performed out of window, done by telephone instead of on-site, not done, etc).

Based on how the visit was affected by the global pandemic, all visits will have a variable indicating how the visit was performed:

- Visit not done at all
- Visit done by video call
- Visit done by telephone
- Visit done at different time point than planned / out of window

Additionally, for visits that are affected by COVID-19, all assessments that are missing will be flagged as missing due to COVID-19. Further, the specific reason of missing data will be captured as the following flags:

- Confirmed COVID-19 infection
- Suspected COVID-19 infection
- General circumstances around COVID-19 without infection
- Other

A summary of number and percentage of subjects with COVID-19 related protocol deviations and COVID-19 related device protocol deviations by treatment group and visit will be provided for the SS-a and SS-s. This summary on COVID-19 related protocol deviations will also be repeated by country.

A by-site, subject and visit listing of COVID-19 related protocol deviations along with a listing of COVID-19 related device protocol deviations will be provided.

## 6 DEMOGRAPHICS AND OTHER BASELINE CHARACTERISTICS

All summaries detailed in this section will be performed on the SS-a and SS-s and by PS0014 treatment group.

### 6.1 Demographics

Demographic variables will be summarized by PS0014 treatment group and all bimekizumab treated subjects.

The following continuous variables will be summarized using descriptive statistics (number of subjects, mean, SD, minimum, median and maximum).

- Age at the time of feeder study entry (years)
- Height (cm)
- DV0002 Baseline Weight (kg): will be derived from the weight from the last visit of the feeder study for 1mL device cohort and 2mL cohort subjects.
- DV0002 Baseline BMI (kg/m^2)
- BMI (kg/m^2) will be calculated as:

$$BMI = \frac{\text{Weight (kg)}}{(\text{Height (m)})^2}$$

The following categorical variables will be summarized using frequency counts and percentages.

- Age group ( $\leq 18$ , 19- $<65$ ,  $\geq 65$  years)
- DV0002 Baseline Body Weight ( $\leq 100$ kg,  $>100$ kg)
- BMI ( $<25$  kg/m^2, 25 to  $<30$  kg/m^2,  $\geq 30$  kg/m^2)
- BMI tertiles ( $\leq t1$  kg/m^2,  $>t1$  kg/m^2 to  $\leq t2$  kg/m^2,  $>t2$  kg/m^2) based on the respective PK-PPS populations (PK-PPS-s, PK-PPS-s)
- Gender
- Race
- Ethnicity
- Country

By-subject listings of demographics will be provided.

## 6.2 Other Baseline characteristics

Baseline characteristics will be summarized by treatment group and overall.

Generally, the following continuous variables will be summarized using descriptive statistics (number of subjects, mean, SD, minimum, median and maximum).

- Duration of disease (years)

Duration of disease (years) will be calculated as:

$$\text{Disease Duration} = \frac{(\text{Date of randomization in DV0002} - \text{Date of onset of Plaque Psoriasis}^1)}{365.25}$$

If the date of onset of plaque psoriasis is partial, it should be imputed to the most recent feasible date (ie, last day of the month if only day is missing, or the last day of the year if day and month

are missing). Note that if the date of randomization is missing then the duration of disease will be derived using the date of screening.

The following categorical variables will be summarized using frequency counts and percentages.

- Duration of disease (<median, ≥median).

### **6.3 Medical history and concomitant diseases**

Previous and ongoing medical history collected at the start of the feeder study will be based on SS-s and SS-a and summarized by treatment groups, system organ class (SOC) and preferred term (PT) using MedDRA®. Medical history and psoriasis history will be included in the summary tables and listings for medical history. Medical procedures are not coded.

Previous and ongoing medical history along with the updated medical history collected at the end of the feeder studies will be presented in a by-subject listing for SS-s and SS-a, respectively.

### **6.4 Prior and concomitant medications**

Concomitant medication details are collected at each visit of DV0002. Concomitant medications are medications taken at least one day in common with the DV0002 study medication dosing period (DV0002 Baseline to DV0002 Week 16).

All concomitant medication will be listed for SS-s and SS-a, respectively.

Concomitant medication which started before DV0002 Week 16 and were ongoing at the data cut off will be included with the status remaining as ongoing. Concomitant medication which were ongoing at DV0002 Week 16 but with an end date before the data cut off will be included with their end date as recorded.

For 2 ml phase analysis, concomitant medications include those started on or before the later of the final contact date or (the last injection date + 7 days).

## **7 MEASUREMENTS OF TREATMENT COMPLIANCE**

During the Treatment Period of this study, IMP administration (either self-administration or study personnel-administration) will be performed in the clinic and observed by the Investigator or his/her designee; monitoring subject compliance is therefore not applicable.

## **8 EFFICACY ANALYSES**

No efficacy summaries are planned for the DV0002 substudy.

## **9 PHARMACOKINETICS AND PHARMACODYNAMICS**

### **9.1 Pharmacokinetics**

The statistical analyses of the PK data will be descriptive in nature and will be summarized using the relevant device-specific population (PK-PPS-s or PK-PPS-a). Data will be analyzed overall for each device by injection type (self-administered or study personnel-administered), by injection site (abdomen or thigh), and by BMI category. The BMI categories will be defined into three tertiles within each device arm PK-PPS analysis set and device cohort and derived from subjects' DV0002 Baseline BMI values.

To allow for an analysis of PK trough levels for bimekizumab administration via self-injection or via study personnel administration, pre-dose PK samples will be taken throughout the DV0002

substudy. For the Q4W dose regimen, PK trough levels will be determined based on pre-dose PK sampling at DV0002 Baseline and DV0002 Week 8 for the study personnel administration and at DV0002 Week 4 and DV0002 Week 12 for the self-administration trough levels, respectively. For the Q8W dose regimen, PK trough levels will be determined based on pre-dose PK sampling at DV0002 Baseline for the study personnel administration and at DV0002 Week 8 and DV0002 Week 16 for the self-administration trough levels, respectively. For the 1ml device cohort, DV0002 Baseline PK samples are the PK samples from the last visit of the feeder studies.

For the analysis of PK trough levels by injection site (abdomen or thigh) and by BMI category (by tertiles), self-administration PK trough levels and study personnel administration PK trough levels will be used.

PK samples for self-administration where the injection was done by site personnel or caregiver will be listed but not be used for summary statistics. PK samples for personnel administration where the injection was done by the subject will be listed but not be used for summary statistics.

Only pre-dose (trough) concentrations will be included while summarizing tables and figures. If the dosing for a visit is +/- 7 days out of window then the plasma concentration from that visit and all subsequent visits will be excluded from the PK summary. PK samples collected after dosing will be excluded from summary statistics.

PK summaries will be based on observed values. No imputation will be used. However, if plasma concentration measurements are below the level of quantification, then for calculation of the derived statistics the result will be set to 1/2 of the lower level of quantification (LLOQ). Descriptive statistics including geometric mean, geometric coefficient of variation, and geometric mean 95% CI if applicable will be calculated if at least 2/3 of the values of interest are above the LLOQ. If this is not the case, only median, minimum, and maximum will be presented.

Boxplots of plasma concentration will be presented by visit and by treatment group.

All PK results will be listed.

In addition, the PK results from all subjects not in PK-PPS-s or PK-PPS-a will be listed based on the SS-a and SS-s.

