Table 5-1: Bimekizumab administration schedule visits in DV0002 substudy 1mL device cohort

| Dose Regimen | Baseline | Week 4 | Week 8 | Week 12 | Week 16 |
|--------------|----------|--------|--------|---------|---------|
| 320mg Q8W | S | NA | S | NA | SP |
| 320mg Q4W | S | SP | S | SP | SP |

bimekizumab-AI-1mL=1mL bimekizumab auto-injector; bimekizumab-SS-1mL=1mL bimekizumab safety syringe; NA=not applicable; Q4W=every 4 weeks; Q8W=every 8 weeks; S=subject performing self-injection using the investigational device; SP=study personnel performing injection using the 1mL pre-filled syringe
 Note: For S injections, the 320mg bimekizumab dose will be administered as two 160mg injections (using 2 bimekizumab-SS-1mL or 2 bimekizumab-AI-1mL). For SP injections, the 320mg bimekizumab dose will be administered as two 160mg injections (using prefilled syringes). Both injections will be administered in the same manner (eg, both self-administered injections or both study personnel-administered injections), but each injection will be administered at a separate injection site and rotation between injection sites should be observed.

Note: For the 1mL device cohort, visits in the DV0002 substudy correlate with the same visit in the PS0014 study (ie, the DV0002 Baseline Visit is the PS0014 Baseline Visit). Dose regimen will be assigned at Baseline, and the same interactive response technology will be used for both studies.

The bimekizumab administration schedule optimizes the collection of PK trough level data within the constraints of a short treatment period and a Q4W and Q8W dosing regimen. At Weeks 4, 12, and 16, subjects on the Q4W dosing regimen will be injected by study personnel with 2 injections each of 160mg bimekizumab using a 1mL PFS (ie, the same device as that used

in PS0014). For these subjects, the Q4W administration schedule will provide PK trough data associated with injection by:

- Study personnel using the 1mL PFS from PK samples collected (before self-injection) at Baseline and Week 8 (ie, PK data from 2 timepoints)
- Subject self-injection using the assigned device from PK samples collected (before injection by study personnel) at Week 4 and Week 12 (ie, PK data from 2 timepoints)

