14.4 Planned pharmacokinetic analyses

The statistical analyses of the PK data will be descriptive in nature and will be summarized using the relevant device-specific population (PK-PPS-s or PK-PPS-a). Data will be analyzed overall for each device by injection type (self-administered or study personnel-administered), by injection site (abdomen or thigh), and by BMI category. Three BMI categories will be defined based on tertiles derived from subjects' Baseline BMI values within the device-specific population (PK-PPS-s or PK-PPS-a).

To allow for an analysis of PK trough levels for bimekizumab administration via self-injection or via study personnel administration, pre-dose PK samples will be taken throughout the DV0002 substudy. For the Q4W dose regimen, PK trough levels will be determined based on pre-dose PK sampling at DV0002 Baseline and Week 8 for the study personnel administration and at DV0002 Week 4 and Week 12 for the self-administration trough levels, respectively. For the Q8W dose regimen, PK trough levels will be determined based on pre-dose PK sampling at DV0002 Baseline for the study personnel administration and at 8 weeks after training (DV0002 Week 8) and DV0002 Week 16 for the self-administration trough levels, respectively. For the analysis of PK trough levels by injection site (abdomen or thigh) and by BMI category (by tertile), only self-administration PK trough levels will be used.

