### 1mL Device Cohort

For the 1mL device cohort, to maintain blinding in the PS0014 feeder studies, DV0002 will recruit subjects who were administered bimekizumab 320mg (Q4W or Q8W) and subjects who were administered placebo or ustekinumab in the PS0014 feeder studies. A total of 100 subjects (50 subjects per device arm) are planned for PK trough level analyses, but these analyses can only be performed on subjects who do not change their bimekizumab dose or dosing regimen (ie, 320mg bimekizumab Q4W or Q8W) between the PS0014 feeder studies and the DV0002 substudy. The DV0002 substudy will therefore enroll approximately 200 subjects (to compensate for subjects with bimekizumab dose changes) to ensure that 100 subjects are available for PK trough analysis.

Subjects who enroll in the DV0002 substudy 1mL device cohort will be randomly assigned to the bimekizumab SS 1mL or the bimekizumab AI 1mL device arms (each device arm will consist of approximately 100 subjects). Within each device arm, subjects will be divided into tertiles by BMI; there will be approximately 33 subjects per tertile, which is expected to yield approximately 16 to 17 subjects per tertile who are evaluable for steady state trough PK level analyses.

Subjects are evaluable for steady state trough PK level analyses, if they enter PS0014 on the same drug and dose as completing the feeder study and if they receive the drug at least 16-20 weeks before PS0014. The second condition is automatically fulfilled. Each subject in the feeder study will receive more than 20 weeks of the same treatment in the maintenance phase except escape subjects from PS0013 which are excluded from DV0002 enrollment.

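### In Q4W subjects the Week 8 trough is classed as a study-personnel trough although up to a quarter of it is drug self-injected at Baseline; combining it with Baseline would shrink the visible difference between injection types

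*SAP*

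**What the plan says.** SAP 9.1 plans a descriptive summary of troughs for each device by injection type. For Q4W it takes "PK sampling at DV0002 Baseline and DV0002 Week 8 for the study personnel administration", and "DV0002 Week 4 and DV0002 Week 12 for the self-administration trough levels, respectively". Protocol 14.4 makes the same assignment ("pre-dose PK sampling at DV0002 Baseline and Week 8 for the study personnel administration"), and Protocol 5.1 repeats it for both device cohorts.

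The dosing order is in Protocol Table 5-1, with the same pattern in Table 5-2. For Baseline and Weeks 4, 8, 12 and 16 the row reads "320mg Q4W | S | SP | S | SP | SP", where S is self-injection and SP is injection by study personnel.

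The SAP's rule for personnel samples looks only at who gave the injection: "PK samples for personnel administration where the injection was done by the subject will be listed but not be used for summary statistics". Nothing is said about drug left from earlier doses.

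SAP 2.4 gives the only indication of how slowly the drug accumulates. In the 1mL cohort, subjects count as evaluable at steady state only "if they receive the drug at least 16-20 weeks before PS0014".

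**The concern.** Each trough is labelled by the last injection alone. A drug that needs 16-20 weeks to reach steady state does not clear in 4 or 8 weeks, so the Week 8 sample still holds drug from the Baseline self-injection. If a device delivers less than the prefilled syringe (PFS), it lowers the Week 8 value as well, and that value sits in the group it would be compared with. The effect is always to make the two injection types look more alike.

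Trough levels by self-injection and by personnel injection are a stated objective (Protocol 3.3, SAP 2.1.3), and the 1mL sample size was set to secure subjects evaluable for trough PK (Protocol 14.10). A reader of the injection-type table will compare the two groups, and nothing in the plan warns that one holds part of the other.

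**Working it through.** The documents state no half-life, carry-over share or effect size, so there is no planned figure to reproduce.

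**Inputs**
- From the documents: the Q4W order S, SP, S, SP (Tables 5-1 and 5-2); a 4-week interval; an unchanged regimen beforehand, so steady state at Baseline (PK set definitions, SAP 3.6.1.4 and 3.6.2.4); and the 16-20 weeks of SAP 2.4.
- Assumed: linear kinetics; 16-20 weeks equals 4-5 half-lives, so a half-life of 16/5 = 3.2 to 20/4 = 5 weeks, central value 4; and personnel doses given by the PFS, as the protocol states.

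**Shares.** Let r = 2^(-4/half-life in weeks) be the fraction of a trough left 4 weeks later. At steady state the last dose supplies 1 - r of a trough, the dose before it (1 - r)r, and all older doses r². The self-injected share is therefore:
- Week 4: 1 - r
- Week 8: (1 - r)r, from the Baseline dose
- Week 12: (1 - r)(1 + r²), from the Week 8 and Baseline doses

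(1 - r)r is largest at r = 0.5, where it equals 0.25, so a quarter is a ceiling.

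**Visible difference.** If a device delivers a fraction 1 - d of the dose, each trough relative to Baseline is 1 - d × (self-injected share). Take the self value as the mean of Weeks 4 and 12. As a multiple of d, the difference is mean(Week 4 share, Week 12 share) against Baseline alone, and that figure minus half the Week 8 share against the mean of Baseline and Week 8.

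| Half-life (weeks) | 3.2 | 4 | 5 |
|---|---|---|---|
| r | 0.420 | 0.500 | 0.574 |
| Self-injected share, Week 4 | 0.580 | 0.500 | 0.426 |
| Self-injected share, Week 8 | 0.244 | 0.250 | 0.244 |
| Self-injected share, Week 12 | 0.682 | 0.625 | 0.566 |
| Difference ÷ d, Baseline alone | 0.631 | 0.5625 | 0.496 |
| Difference ÷ d, Baseline + Week 8 | 0.509 | 0.4375 | 0.374 |
| Loss from including Week 8 | 19% | 22% | 25% |

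The loss does not depend on d.

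**Example** (half-life 4 weeks, assumed d = 0.2). Relative troughs are Baseline 1.000, Week 4 0.900, Week 8 0.950 and Week 12 0.875, so the self mean is 0.8875.
- Against Baseline and Week 8 combined: 0.975 - 0.8875 = 0.0875.
- Against Baseline alone: 1.000 - 0.8875 = 0.1125.
- Loss: 0.025/0.1125 = 22%.

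**Wider range.** For half-lives of 14 to 56 days the Week 8 share is 19-25% and the loss 12-28%. At 10 days the share is 12.3%. Adding first-order absorption changed the shares by no more than about 0.0002. The ±7 day dosing window shifts the shares for individual subjects.

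**Precision.** Assume equal variances σ² and equal correlations ρ between visits. A within-subject contrast of two self troughs with two personnel troughs has variance σ²(1 - ρ)(1/2 + 1/2). With Baseline alone it is σ²(1 - ρ)(1/2 + 1). The standard error rises by √1.5 = 1.22, that is 22%, at any ρ. The visible difference rises by 1/(1 - loss), that is 24-33%. Signal relative to noise therefore improves by only about 1-8%. At a 14-day half-life it falls by about 7%.

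**The case against.** The contrast above is not in the plan. No difference, ratio, margin or test is specified. SAP 9.1 assigns visits to injection types but does not say that Baseline and Week 8 are averaged. Boxplots are by visit and all PK results are listed, so the two can be seen apart. For Q8W the personnel trough is Baseline alone, so a comparison with an uncontaminated reference already exists. All of this stands, and it limits the harm to how the Q4W injection-type summary is read.

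The size rests on an assumed half-life, and the 16-20 weeks is an evaluability rule, not a kinetic estimate. That stands too. The direction needs only that some of a dose remains after 8 weeks.

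The schedule itself dilutes more than the label does. At a 4-week half-life, personnel-injected drug makes up 50% of the Week 4 self trough and 37.5% of the Week 12 one. A 20% shortfall shows as 11.25 points even against Baseline alone. Separating Week 8 recovers 2.5 points, so the footnote matters as much as the row.

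Baseline alone has its own weakness. In the 1mL cohort that sample comes from the last feeder-study visit, so injection type would be confounded with study and time. This is a good reason to keep Week 8 in the table, though not to merge it with Baseline.

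A reader might infer that the plan could hide a device that under-delivers. The documents do not support this: complete delivery is judged directly in the primary endpoint by inspecting the used device (Protocol 4.1.1, SAP 11.1), and structural integrity and function are summarized separately (SAP 11.3.4).

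**Conclusion.** The point holds for Q4W subjects in both cohorts. The Week 8 personnel trough contains self-injected drug: at most 25% at steady state, 24-25% if 16-20 weeks means 4-5 half-lives, and 19-25% for half-lives of 14-56 days. If it is combined with Baseline, the visible difference between injection types shrinks by about 19-25% over the assumed range of 3.2-5 weeks, always toward no difference. These figures assume linear kinetics, steady state and the protocol's statement that personnel use the 1mL PFS.

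Two stronger readings are tempting. One is that a quarter is an established fact; it is a ceiling, and the documents contain no half-life. The other is that the plan definitely pools the two visits; it groups them under one injection type but never states how they are summarized.

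This is a cheap improvement to a descriptive secondary-tier summary. It does not touch the primary or secondary outcome.

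**What to change.** In SAP 9.1, for Q4W:
- State that Baseline and Week 8 are not combined in the injection-type summary.
- Use Baseline as the main personnel reference.
- Report Week 8 in its own row, labelled *personnel injection after a self-injected dose*, so that a within-substudy personnel trough stays visible.
- Add a footnote that alternating injectors make both the personnel troughs after Baseline and the self troughs mixtures, so trough ratios understate the per-dose difference.

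Because Protocol 14.4 and 5.1 count two personnel timepoints, record the departure in SAP 3.10.

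Reconcile the device used by personnel. SAP 2.3.2 says the investigational device at Weeks 4, 12 and 16; the protocol (5.1, Tables 5-1 and 5-2) says the 1mL PFS. This decides what the Week 8 trough represents. Under the SAP wording the Week 4 dose would also come from the device, and the device-delivered share at Week 8 would be 1 - r², or 67-82% over the assumed range.

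The cost is SAP wording, one table row and a footnote, with no new samples or visits. The price is precision: the standard error of a paired Q4W contrast rises about 22%, roughly offset by the 24-33% larger visible difference. The gain is less bias, with little change in the ability to detect a difference.
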